Throughout the course of this study, we will provide for protection of human subjects. All protocols will be submitted for review and approval to the Colorado Multiple Institution Review Board (COMIRB). All personal data will be kept secure with personal identifiers and study identification numbers maintained in separate, secure, databases. Only the PI and Co-Is will have access. The proposed study is designed to women and overall, the findings of this study may potentially impact the health and wellbeing of women and children.

We have also designed the assessment procedures to minimize burden on participants. Participants will be compensated \$30 per survey completion (T1 and T3; \$60 total/participant). Participants will also receive tickets for a random drawing and chance to receive free diapers for their participation in T2 data collection. Pregnant participants in the MBMM+ intervention group will also receive a yoga mat and pedometer, and both control and intervention groups will receive drawings for free diapers. These types of incentives and amounts are consistent with our other studies at UCH. In addition to the yoga mat and pedometer, the intervention group participants will have the opportunity to keep a Fitbit. If participants attend all sessions 8-16, they will get to keep a Fitbit at the end of the program following post-data collection. If participants in the intervention program attend all but two sessions from sessions 8-16, they will be entered into a raffle for a Fitbit to keep at the end of the program following post-data collection.

F. Data Analysis Plan:

We will use latent growth curve models to separately examine intervention effects on 1) moderate-intensity exercise assessed by the Fitbit and 2) EGWG. These models will then be expanded to examine secondary outcomes (e.g., physical activity, mood, sleep quality, delivery outcomes) and mediators (e.g., exercise self-efficacy, social support, and behavioral skills). For all models, we will control for patient age, ethnicity, parity, risk status, and SES. Primary analyses will be conducted as intent-to-treat, although exploratory as-treated analyses may also be used. Analyses will be conducted primarily using SAS Version 9.2 and Mplus Version 6.0. In closing, the study's proposed approach

is scientifically sound using a tight, randomized controlled trial framework to reduce study bias and increase likelihood of reproducibility.

G. Summarize Knowledge to be Gained:

This is an important and fundamental study that needs to be conducted to meet the need for effective, sustainable community-based interventions to reduce EGWG. Because pregnancy is an opportune time to adopt healthy behaviors such as physical activity, there is a definite need for intervention at this time. The MBMM+ intervention has been designed based on feedback from pregnant women from recent formative and pilot work to develop an intervention that is attractive and unique to this population. The intervention includes a strong social support component as our formative work and extant literature clearly demonstrate lower levels of attrition in interventions providing social support. Moreover, the addition of the small group interaction after each session will provide further opportunity to build rapport and strengthen interpersonal support and a sense of group membership. Third, self-regulation techniques that support maintenance of physical activity and its interrelatedness of mood and sleep will be used. All of these supports can show successful community-based interventions to reduce EGWG.

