COMIRB Protocol

COLORADO MULTIPLE INSTITUTIONAL REVIEW BOARD
[name] [contact] [contact]

Protocol #: 19-1366

Project Title: My Baby My Move+

Principal Investigator: [name]

Version Date: 5.6.21

I. Hypotheses and Specific Aims:

Statement of Purpose: The proposed study will implement and test the feasibility of a theoretically-based (e.g., social cognitive theory), peer-led wellness intervention, “My Baby My Move+” (MBMM+) to reduce excessive gestational weight gain (EGWG) by targeting physical activity, mood, and sleep.

The aims of the proposed research are to:

- Aim 1. Determine feasibility (i.e., acceptability and demand) of the MBMM+ program.
- Aim 2. Examine the impact of the MBMM+ program on EGWG at 12 weeks post-baseline to determine estimates of effect size for a future, larger randomized trial.

II. Background and Significance:

Up to 50% of pregnant women in the U.S. gain weight in excess of the Institute of Medicine (IOM) guidelines (i.e., excessive gestational weight gain (EGWG)). EGWG leads to poor maternal (e.g., pre-eclampsia, gestational diabetes, postpartum weight retention) and child (e.g., preterm birth, large for gestational age weight at birth) outcomes. It also sets the stage for long-term overweight/obesity for both mother and child. There are few efficacious intervention strategies for reducing EGWG and among those, physical activity is one promising strategy. Prenatal physical activity is associated with a variety of health benefits (e.g., reducing risks for gestational diabetes, pre-eclampsia, depression, and body image dysphoria). There is also a need to increase prenatal physical activity as approximately 80% of pregnant women are not meeting recommended levels. One reason for low prenatal activity is that pregnant women are concerned with and lack knowledge/skills about how to safely and effectively participate in physical activity. Increasing knowledge and skills about physical activity may improve prenatal physical activity participation, lower safety concerns, and in turn, reduce EGWG.

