mindfulness, wellness wheel, family/life balance) and sleep (good sleep hygiene, sleep/energy balance) given their inter-relatedness to EGWG and physical activity, 3) add a comprehensive objective assessment of physical activity, 4) add an appropriate comparison group that controls for time and attention (i.e. health education group); 5) add yoga as a programmatic activity component throughout program, and 6) increase participant/peer leader contact time by addition of more small group participant interactions with peer leaders. To do so, we will increase the length of intervention from eight to 12 wks as well as the dose from one session/wk to two sessions/wk.

IV. Research Methods

A. Outcome Measure(s): The Assessment Table (Table 1) displays all primary and secondary outcomes, associated measures, and the timeline of data collection. Data will be collected at four timepoints: T1) baseline, T2) 6-weeks post-baseline, and T3) 12- week post-baseline (i.e. end of intervention) and T4) at time of delivery.

Assessment tools (scale and Fitbit) will be delivered to participants after eligibility is confirmed and after they complete the online consent and baseline survey at a time and location of their choosing. A scale and Fitbit with a brief one-page protocol will be delivered to the participants by the Study Coordinator. Seven-days after delivery, the Study Coordinator will pick up the Fitbit (from all participants) and scale (from control participants). The participants will leave these materials at a specific location for the Study Coordinator. There will be no contact between them. During this time, the Study Coordinator will either drop off a hard copy of the curriculum (or send an electronic copy) as well as incentives for the intervention group participants (yoga mat and pedometer). The team has instituted strict protocols to minimize exposure related to COVID-19. This includes:

- No contact with participants; the Study Coordinator will leave the materials mentioned above at a specific location dictated by the participant (e.g. front porch).
- The Study Coordinator will wear a mask at all times when doing deliveries of assessment and programmatic materials.
- The Study Coordinator will complete a symptoms checklist and take their temperature prior to dropping off assessment and programmatic materials. This will be shared with the PI prior to delivery.

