- The Study Coordinator will keep hand sanitizer in their car and use before and after delivery of assessment and programmatic materials.
- The research team will follow all safety protocols instituted by the University of Colorado regarding COVID-19 and human subjects research.

Weight Gain. Weight will be collected at T1 and T3 for all intervention and control participants. Participants will be asked to record their weight three times on one day and send a picture (via text or email) to a member of the research team during the 7-day assessment week. Individuals will be asked to remove their clothes and shoes and keep on their undergarments and weigh themselves first thing in the morning before they eat anything. Total GWG will be captured three times consecutively and then averaged across these three weight recordings. Total GWG will be compared to the IOM guidelines at T1

and T3 and calculated as: +, -, or 0 with respect to the guidelines (based on each woman's pre-pregnancy BMI-determined GWG category) such as GWG above the guidelines (+), below guidelines (-), or within the guidelines (0) [39]. Participants randomized to the intervention group will also be given a TANITA scale to measure weight at home daily (the research team will send weekly reminders via email or text). Women will step on the scale and note their weight on a tracking log at the same time each day. Participants will email copies of tracking logs weekly to the study coordinator. Please see appendix for tracking log.

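### Weight gain is scored against guideline limits at T1 and T3 with no stated limit for gestational age, and the analysis plan neither fixes the scale of the outcome nor adjusts for gestational age

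*Combined protocol and SAP*

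**What the plan says.** Aim 2 (section I) is to examine the effect of the programme "on EGWG at 12 weeks post-baseline to determine estimates of effect size for a future, larger randomized trial".

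Section IV.A, Weight Gain, contains the only operational definition in the text available. "Weight will be collected at T1 and T3 for all intervention and control participants", and then "Total GWG will be compared to the IOM guidelines at T1" "and T3 and calculated as: +, -, or 0 with respect to the guidelines". The limit depends on each woman's pre-pregnancy BMI category, and gestational age is not mentioned.

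The visits are set earlier in IV.A: "T3) 12- week post-baseline (i.e. end of intervention) and T4) at time of delivery". Section IV.B describes screening at 6 to 12 weeks. The inclusion criteria in IV.D admit women below 13 weeks, and women at 13 to 16 weeks whose gain so far is under a cap. Maternal weight at delivery and gestational age are collected by self-report (IV.A, Delivery outcomes), but they are not tied to the +/0/- score.

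Section IV.F says "We will use latent growth curve models to separately examine intervention effects on" Fitbit-measured exercise and EGWG, without giving the scale of EGWG. It adds: "For all models, we will control for patient age, ethnicity, parity, risk status, and SES". Section IV.B sizes the trial on Cohen's d. IV.A also says "The Assessment Table (Table 1) displays all primary and secondary outcomes, associated measures, and the timeline of data collection"; that table is not in the text I could read.

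**The concern.** An analyst working from this text has to make two choices that it does not settle.

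The first is the limit that applies at T1 and T3. The term total GWG, with a limit set by BMI category alone, suggests the whole-pregnancy range. On that reading, gain to mid-pregnancy is judged against a limit meant for term, so + would be rare at T3 and would say little about who is on course to exceed the guidelines.

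The second is what enters the model: the three-level category or continuous gain. IV.A points one way, and IV.B and IV.F the other.

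Under either choice, women are weighed at T3 at quite different stages of pregnancy, and the listed covariates leave gestational age out. Risk status is on the list but is not defined. At stake is how useful Aim 2's effect size will be as a planning figure for the larger trial.

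**Working it through.** **1. The plan's own figure.** Inputs from IV.B: d = 0.63, alpha 0.05, power 0.80. Two-sided comparison of two means: n = 2(1.960 + 0.842)²/0.63² = 39.6, so 40 per arm; 40/(1 - 0.20) = 50 enrolled. Both stated figures reproduce. (The t-based version gives 40.5, so 41, and 79.5% power at 40 per arm.) This is a calculation for a continuous outcome.

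**2. Gestational age at T3.** Entry week plus 12: 6 + 12 = 18, 12 + 12 = 24, 16 + 12 = 28. On the IV.B window T3 is at 18 to 24 weeks; with the IV.D upper end it reaches 28 weeks, or just under 29 for entry at 16 weeks 6 days. The spread is 28 - 18 = 10 weeks. Any lag between screening and baseline shifts T3 later.

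**3. What the whole-pregnancy reading would do (illustration of one unconfirmed reading).** The documents give no gain distribution, so these inputs are assumed, except that 50% exceed the limit at term, the top of the background figure in section II.
- Final gain G is Normal with mean 1 and SD = CV; CV 0.25, 0.35 or 0.45. One limit U for all women; with 50% exceeding, U = 1.
- Fraction f of final gain reached by week w: either w/40, or 10% by week 13 and then linear to week 40. At 24 weeks f = 0.60 or 0.47; at 28 weeks f = 0.70 or 0.60.
- P(+) = P(G > U/f). Highest cell at 28 weeks: (1/0.70 - 1)/0.45 = 0.952, giving 17%. Lowest: (1/0.60 - 1)/0.25 = 2.67, giving 0.4%.

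| T3 | P(+), range over the grid |
|---|---|
| average over 18-24 weeks | 0.0% to 2.7% |
| average over 18-28 weeks | 0.0% to 6.3% |
| at 28 weeks | 0.4% to 17% |

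In 40 women the 18-28 week average gives at most 40 x 0.063 = 2.5 scoring +, against 20 at term. These ranges are not bounds: every woman is assumed to accrue the same fraction of her final gain. If the relative spread at T3 were wider (assumed CV 0.60), P(+) at 28 weeks would be 13% to 24%.

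**4. Why the scale matters even at a 50% rate.** Assume a Normal outcome shifted by 0.63 SD and analysed as + versus not +. The intervention rate is then Phi(0 - 0.63) = 0.264. With 40 per arm, pooled rate 0.382, null SE = sqrt(2 x 0.382 x 0.618/40) = 0.1086 and alternative SE = sqrt((0.25 + 0.194)/40) = 0.1054. Power = Phi((0.236 - 1.96 x 0.1086)/0.1054) = 0.585, against 0.804 for the continuous outcome by the same Normal approximation. Keeping all three levels should lose less than this.

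**5. What leaving out gestational age costs.** Assumed: gain of 0.1-0.2 kg per week before week 13 and 0.3-0.6 after, entry uniform over 6-16 weeks, other SD of T1-T3 gain 2-5 kg. The SD of gain due to entry age alone is then 0.23 to 1.17 kg.
- Upper corner: share of variance = 1.165²/(1.165² + 2²) = 25.3%. A linear term captures 94% of this, or 23.9%. Then d = 0.63/sqrt(1 - 0.239) = 0.722 and power at 40 per arm is 89.1%.
- Lower corner: 0.233²/(0.233² + 5²) = 0.2%, and power stays at 79.5%.
- With entry at 6-12 weeks the share is 0.1% to 15.8%.

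**The case against.** The strongest reply is that the whole-pregnancy reading may not be what the authors mean. They score the category at T1 as well, and in the model above + would almost never occur there: at week 16 the highest cell is (1/0.40 - 1)/0.45 = 3.33, or 0.04%. A score that is empty by construction makes little sense. The inclusion criteria also show the authors using gain caps tied to 13-16 weeks. Both point towards a limit for the time of weighing. This stands: the under-count is conditional on a reading that the documents do not confirm, and neither the cited guideline nor the assessment table can be consulted here. It does not close the gap, because the text states no such limit.

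Secondly, Cohen's d and growth curves already lean towards a continuous outcome. That is fair, and it is why a reader should not infer that Aim 2 is left without an effect size: weights at T1 and T3 are planned for every woman. But the lean is an inference, and the only definition available is a category.

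Thirdly, the covariate is optional in a feasibility study. It may indeed be worth almost nothing in precision, but it is nearly free.

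Finally, replacing the category with T1-T3 gain alone would drop gain before baseline and the reference to the guidelines that makes gain excessive. This stands, and it shapes the fix.

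**Conclusion.** The point holds in a limited form. The stated rule gives no limit for gestational age at visits that fall at about 18 to 28 weeks. The defined outcome (a category) does not match the outcome that the sample size and model fit (continuous), and gestational age is missing from the covariates. These deserve correction before the analysis, because Aim 2 exists to supply a planning effect size.

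The size is modest or conditional. Adjustment for gestational age is worth between nothing and about 10 points of power at 40 per arm (79.5% to 89%), on assumed gain rates and SDs. The + rates illustrate one unconfirmed reading on assumed distributions.

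Three stronger conclusions are tempting and are not supported:
- That EGWG will certainly be under-counted. This depends on the whole-pregnancy range being the one applied.
- That the larger trial will be wrongly sized. No passage proposes to size it on the proportion scoring +.
- That the comparison is biased. The same rule applies to both randomised arms, so no between-arm bias is expected.

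The plan's sample-size arithmetic is not in error.

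**What to change.** In IV.A and IV.F:

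1. Score any category at T1 or T3 against the guideline limit for gestational age at weighing. Apply the whole-pregnancy +/0/- category only to delivery weight (T4), as a secondary outcome.
2. For the Aim 2 effect size, analyse weight gain at T3 as a continuous outcome, in line with the Cohen's d in IV.B. Adjust for T1 weight or gain to T1, gestational age at T1, and pre-pregnancy BMI group. Report the gestational-age-specific category beside it, so that the reference to excessive gain is kept.

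The cost is revised wording and slightly more analysis. Gestational age is already needed for eligibility and BMI category for scoring, and delivery weight is already collected. Two downsides should be acknowledged: the whole-pregnancy category becomes secondary and rests on self-reported delivery weight, and the continuous measure does not by itself refer to the guidelines.

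Separately, the entry windows in IV.B and IV.D should be reconciled, since they set the range of gestational age at T3.

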participation in the program (to what extent they were satisfied with the program and parts of the program they enjoyed and parts they think could be stronger, etc). The interviews will be approximately 45 minutes long and you will be compensated \$30. Up to 15 women will be invited to participate in an interview. Due to COVID-19, the trial will be run two times; a remote pilot of the trial will be run in the Fall of 2020 (n=30), followed by a larger in-person trial (pending COVID-19) in the Spring of 2021 (n=70)

Interviews with participants will be conducted after the pilot trial (Fall 2020) in addition to after the full trial (Spring 2020).

B. Description of Population to be Enrolled:

We anticipate eligibility screening for pregnant women (6 through 12 weeks) to take approximately 5-10 minutes to complete. The time window for gestational age recruitment was selected based on our formative work [25] [26] that suggests that in order to impact EGWG early intervention is critical. The first 4 weeks of the intervention will consist of educational materials as women may not want to participate in physical activity until near the end of first trimester when their risk for miscarriage drops and the mother tends to feel better physically. The experiential component (i.e., walking and yoga) will start in week 5. In order to extend our recruitment window, we will create rolling recruitment opportunities with women entering into the program from weeks 1 through weeks 6 (weeks 1-4 electronic materials; weeks 5-6 zoom sessions begin). All women will receive the electronic materials for weeks 1-4 before starting the zoom group sessions in week 5. For those women who start the zoom sessions in week 6, they will receive an additional session (material from original week 5) at the end to ensure all women receive 16 sessions (8 weeks of zoom sessions). Women will be recruited from the University of Colorado Clinics, clinics in Denver Metro and surrounding areas as well as social media (e.g. facebook and instagram). We will work with providers to help with recruitment of women in need of intervention for EGWG.

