Sample Size. In terms of intervention effects on EGWG, results have been variable across studies, with average intervention effects being small to moderate. In terms of physical activity, our preliminary work with the original MBMM showed an effect roughly equivalent to Cohen's $d = 0.69$. This effect falls into the moderate range, similar to higher-impact interventions on EGWG [27]. Based on these two effect ranges, we estimated effect size to detect effects of $d > .63$, a medium effect, for the proposed MBMM+ intervention. Using this effect size, $\alpha = .05$, and $1-\beta = .80$, a sample size of 40 per arm (80 total) would be adequate to detect medium effects in EGWG, exercise, and other outcomes. We propose enrolling 50 per arm to account for up to 20% attrition and to allow for power to detect potentially smaller effects for EGWG. This level of power is expected to also be adequate for detecting changes in mediators, which have previously been observed to be more powerfully affected by the MBMM intervention than physical activity.

Due to COVID-19, the trial will be run two times; a remote pilot of the trial will be run in the Fall of 2020 (n=30), followed by a larger in-person trial (pending COVID-19) in the Spring of 2021 (n=70)

C. Study Design and Research Methods

Intervention Group:

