Inclusion criteria – The population of interest includes English-speaking, pregnant (<13 weeks gestation; or 13-16 weeks gestation and has gained less than 10 lbs in total for women of normal pre-pregnancy weight or less than 5 lbs for overweight/obese) primiparous women, aged 18-46 years, reside in Denver, CO and have medical clearance to exercise during pregnancy. Exclusion criteria include multiparous and having conditions that preclude them from exercising (i.e. HCP has restricted patient from engaging in exercise according to AGOG's absolute contraindications to exercise (e.g. haemodynamically significant heart disease, restrictive lung disease, incompetent cervix/cerclage, persistent second or third trimester bleeding, placenta previa after 26 weeks gestation, premature labor during the current pregnancy, ruptured membranes, and pregnancy induced hypertension).

Protection Against Risk. Every effort will be made to ensure the protection of participants against risk. First, participation is voluntary and participants may refuse to participate or withdraw from the study at any time. Second, participants do not waive any legal rights by consenting to the study. Third, the Principal Investigator and program manager will be

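### Two entry rules conflict (6 to 12 weeks' gestation, or up to 16 weeks with a weight-gain cap), and gestational age at entry, which fixes when T3 falls in pregnancy, is not in the analysis model

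*Combined protocol and SAP*

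**What the plan says.** Section IV.B (Description of Population to be Enrolled) states: "We anticipate eligibility screening for pregnant women (6 through 12 weeks) to take approximately 5-10 minutes to complete". The next sentence treats this as the recruitment window and gives its basis, namely formative work that "suggests that in order to impact EGWG early intervention is critical".

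The inclusion criteria in section IV.D define eligible pregnancies differently: "<13 weeks gestation; or 13-16 weeks gestation and has gained less than 10 lbs in total for women of normal pre-pregnancy weight", with a 5 lb limit for overweight or obese women. There is no lower limit on gestation, and no reason is given for the added weeks.

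Sections I and IV.A place the EGWG assessment (T3) 12 weeks after baseline. Section IV.F fits growth curve models adjusted for age, ethnicity, parity, SES and risk status. Gestational age at entry is not listed. The randomisation paragraph in section IV.D describes assignment from a pre-generated table and mentions no stratification.

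**The concern.** Eligibility text decides who is randomised, so two rules that admit different women leave the study population undefined. The conflict also touches the scientific argument. Section IV.B justifies its window on the ground that "in order to impact EGWG early intervention is critical", and section IV.D goes beyond that window without comment.

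The consequence for analysis is timing. Follow-up is counted from baseline, not from conception, so a wider entry window means a wider spread of gestational age when weight gain is assessed. Total gain accumulates with gestation, and section IV.A compares it with the IOM guideline category at T1 and T3 without saying how gestational age enters that comparison. Aim 2 is meant to supply an effect size for a larger trial. A pooled estimate is hard to reuse if the women behind it, and the stage of pregnancy at which they were assessed, are not defined.

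**Working it through.** **1. The two rules side by side**

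| Gestation at entry | Section IV.B | Section IV.D |
|---|---|---|
| Under 6 weeks | outside | eligible |
| 6 to 12 weeks | eligible | eligible |
| 13 to 16 weeks, gain below the cap | outside | eligible |
| 13 to 16 weeks, gain at or above the cap | outside | outside |

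The rules disagree in two of the four rows. The cap is stated for normal-weight and for overweight or obese women; no figure is given for underweight women. The phrase "women entering into the program from weeks 1 through weeks 6" in section IV.B counts weeks of the program, not of gestation, so it is not a third window and does not settle the conflict.

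**2. Gestational age at T3**

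T3 = gestational age at baseline + 12 weeks, taking baseline at the week of entry.

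- Section IV.B window: 6 + 12 = 18 to 12 + 12 = 24 weeks, a spread of 6 weeks.
- Added route in section IV.D: 13 + 12 = 25 to 16 + 12 = 28 weeks.
- Both routes, counted from 6 weeks: 18 to 28 weeks, a spread of 10 weeks. Entry before 6 weeks, which section IV.D allows, would widen it further at the lower end.

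The T3 ranges of the two routes do not overlap (18 to 24 against 25 to 28). For a woman joining in program week 1, the experiential part (week 5) starts about 4 weeks after entry: at about 12 + 4 = 16 weeks at the section IV.B limit, and about 16 + 4 = 20 weeks at the section IV.D limit.

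**3. Does the sample size depend on the window?**

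Inputs from the Sample Size paragraph: d = 0.63, alpha 0.05, power 0.80. Sidedness is not stated; two-sided is assumed, since a one-sided test would give 32 per arm.

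- n per arm = 2 × (1.960 + 0.842)² / 0.63² = 2 × 7.85 / 0.397 = 39.6, so 40. This matches "a sample size of 40 per arm (80 total) would be adequate to detect medium effects in EGWG, exercise, and other outcomes". The t-test version gives 40.5, so 41.
- Power at 40 per arm is 80.4% (normal approximation) or 79.5% (t-test).
- Enrolment: 40 / (1 − 0.20) = 50 per arm, as stated.

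Gestational age is not an input. The paragraph says "we estimated effect size to detect effects of $d > .63$, a medium effect, for the proposed MBMM+ intervention", and it bases that value on the MBMM pilot's physical-activity effect (d = 0.69) and a general range for EGWG interventions. Section III says the pilot ran from the middle or later second trimester into the third, which is later than either entry window. Changing the window therefore alters none of these figures.

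**4. How precise would a by-route effect be?**

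The protocol gives no expected share of later entrants. For illustration, assume even entry over weeks 6 to 16, so 4/11 = 36% come by the later route. Of 40 per arm, that is about 14.5 late and 25.5 early. The 95% half-width on d is approximately 1.96 × √(2/n).

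- Late: 1.96 × √(2/14.5) = ±0.73
- Early: 1.96 × √(2/25.5) = ±0.55
- Pooled: 1.96 × √(2/40) = ±0.44

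**The case against.** The formal inclusion criteria would normally govern, and the section IV.B sentence is mainly about how long screening takes. On that reading this is a leftover in descriptive text. That lowers the weight of the point but does not remove it: section IV.B goes on to call this the gestational window for recruitment and defends it as a deliberate choice, and nothing in section IV.D replaces that defence.

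It can also be said that every woman is followed for the same 12 weeks and that arms are randomised, so a wider entry window does not bias the comparison. That stands. The case for the covariate is precision, protection against chance imbalance in a trial of 50 per arm, and a clear description of the population.

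Two stronger readings are tempting, and the documents support neither.

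- A reader might infer that later entrants dilute the effect and that 80% power is therefore overstated. This needs a late-entry share and a smaller late effect, and the protocol gives neither. With a 36% late share, t-test power at 40 per arm runs from 43% if late entrants gain nothing to about 80% if they respond equally, so the result is whatever one assumes. The pilot behind the effect size was run later in pregnancy than either window, so it offers no support for a smaller late effect.
- A reader might infer that the weight-gain cap biases the result by selecting on the outcome. The cap is applied at screening, before randomisation, and alike for both arms. It changes who is studied, not the fairness of the comparison.

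**Conclusion.** The eligibility conflict is real and needs reconciling. Sections IV.B and IV.D disagree for women under 6 weeks and for women at 13 to 16 weeks below the cap, and the stated rationale covers only the narrower rule. The measurable consequence is timing: the latest T3 moves from about 24 to about 28 weeks' gestation, and the spread grows from 6 to at least 10 weeks if women enter from week 6 on, with no adjustment for gestational age at entry in section IV.F. These figures take the week limits at face value and ignore any gap between screening and baseline.

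The conclusion goes no further. The sample size and power statement stand on their own inputs, the between-arm comparison is not biased, and a by-route effect estimate would be too imprecise (about ±0.73 on d for later entrants under the illustrative share) to carry forward in place of the pooled one.

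**What to change.** - Reconcile sections IV.B and IV.D to one entry rule: lower limit, upper limit, any weight-gain condition and the weight categories it covers. State whether it applies at screening or at baseline, and make the rationale match. Which rule to keep is for the sponsor to decide.
- Record gestational age at entry in the T1 data. Section IV.A lists gestational age only among the delivery outcomes, but either entry rule needs it.
- Add gestational age at entry as a baseline covariate in the EGWG model in section IV.F.
- If the 13 to 16 week route is kept, report the numbers entering by each route in each arm, so that the Aim 2 pooled estimate can be tied to a defined population. Show any effect by route as descriptive only, with its interval.

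The cost is rewording in three sections, one more model term and one row in the baseline table. No extra participants or visits are needed, and the sample size paragraph needs no change on this account.
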